6.8.5. Day 91 (Discharge from Second In-clinic Period)

The following procedures will be done:

- Collect postdose blood sample for PK (approximately 24 hours [± 15 minutes] after the last [Day 90] dose)
- Collect postdose blood sample for analysis of biomarkers of galactose metabolism including galactose, galactitol, and galactose-1-p (approximately 24 hours [± 15 minutes] after the last [Day 90] dose)
- Collect AE and concomitant medications data
- Schedule the EOE Visit for Day 118 (± 2 days) [Only if subject is not directly entering the separate Open-Label Extension study]
- Discharge subject from the CRU and remind subject/caregiver to fast overnight for at least 10 hours on the day before the EOE Visit and have the EOE Visit before breaking the fast

6.9. EOS or EOE Visit (28 Days After the Last Dose)

All subjects will return to the CRU for an out-patient EOS Visit at 28 ± 2 days (Part A [Day 28]; Parts B and C [Day 35]; Parts D and E [Day 60];) after the last dose. For the Part D Extension, the EOE Visit (Day 118 ± 2 days) can be done either as a home health visit or as an out-patient visit to the site. The EOE Visit will not be performed if subjects transition to the separate Open-

Label Extension Study. The study completion for these subjects will be the completion of the Treatment Period at Day 91. The following procedures will be done:

- Update medical history (including current medications)
- Perform physical examination including weight
- Collect fasting blood sample(s) for clinical laboratory testing (hematology, coagulation and biochemistry); and, for female subjects of childbearing potential only, serum pregnancy test
- Collect fasting urine sample for urinalysis, UACR and UPCR
- Measure vital signs
- Conduct 12-lead ECG
- Collect AE and concomitant medication data

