1 in-clinic stay associated with the first dose, a second in-clinic stay associated with the last dose, and home health or in-clinic visits at Months 1 and 2 as indicated in the Schedule of Assessments for Part D Extension ([Appendix F](#)). At any time during Part D Extension, an interview with the patient and caregiver (when appropriate) will be performed to assess the impact of disease. (detailed processes described in a separate Interview Guide). Subjects will return for the EOE Visit at 28 days after the last dose. The EOE Visit will not be required for subjects who transition to a separate Open-Label Extension Study. For these subjects the EOE will be Day 91.

The Schedule of Assessments for Part D Extension is provided in [Appendix F](#). Maximum duration of study participation (Screening through EOE Visit) for an individual subject will be approximately 178 days for a de novo subject and approximately 218 days for a subject who was screened for Part D, completed Part D, and completed Part D Extension without requiring a screening visit for the Part D Extension and without counting any washout period between Part D and Part D Extension.

Table 7: 90-Day Dose Cohort in Subjects with Classic Galactosemia (Part D Extension)

Cohort	Dose	
DE1	AT-007 oral capsule or liquid suspension on Day 1, dose 20 mg/kg (SAD portion), followed by AT-007 oral capsule or liquid suspension QD for a total of 90 days, dose 20 mg/kg (n=up to 21)	placebo (n=up to 7)

n = number of subjects; MAD = multiple ascending dose; QD = once daily; SAD = single ascending dose; TBD = to be determined.

Note: There may be up to 1 additional cohort if the decision is made to test more than 1 dose level. Regardless of whether there is 1 or 2 cohorts, the maximum number of subjects is 28. However, the number of cohorts and total number of subjects may increase if doses above 40 mg/kg are tested in additional cohorts (see [Section 1.4](#)). The overall number of subjects per cohort may be increased to address any potential lost-to-follow-up among subjects treated with either placebo or AT-007.

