9.2.7. Safety Analyses

The evaluation of safety will be based on the occurrence of treatment-emergent adverse events (TEAEs); discontinuations from study drug and/or the study because of AEs; clinical laboratory test results, physical examination findings, vital sign evaluations, and 12-lead ECGs results. All safety endpoints will be summarized descriptively. No statistical inference will be applied to the safety endpoints. Descriptive statistics will be calculated for quantitative safety data and frequency counts will be compiled for classification of qualitative safety data.

AEs will be coded by SOC and PT using MedDRA, version 22.0 or higher.

TEAEs are defined as AEs with onset on or after the date/time of the first dose of study drug.

Safety analyses will be described in detail in the SAP.

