- c: Check-in will occur around 11 am on Day -1. On Day 90, subjects will arrive at the CRU after an overnight fast of at least 10 hours (and before breaking the fast) and before taking study drug. In lieu of overnight stays in the CRU, subjects may stay at a local hotel; subjects will abide by all study guidelines including overnight fasting. The Day 30 and Day 60 visits can be either home health or in-clinic visits.
- d: Discharge from the in-clinic stay will occur after all procedures for that day are done and the subject has stayed in the clinic for at least 24 hours after the first dose.
- e: The EOE visit will be scheduled for 28 (± 2) days after the last dose of study drug. The EOE Visit will not be required if subjects transition to the separate Open-Label Extension Study, in which case the study completion will be considered the completion of the Treatment Period at Day 91.
- f: The informed consent form needs to be signed at the first visit for the extension which may be either the Screening visit or the Day -1 check-in (see footnote b).
- g: All physical examinations will include weight; however, height will be measured only at screening (or prescreening). Prescreening does not include a physical examination (only height and weight).
- h: Vital signs will be measured at Screening (if applicable), every check-in, every check-out, predose (within 60 min before the dose) and 4 hours (± 10 minutes) after the dose on Days 1, 30, 60, and 90, once daily on all other visits, and at the EOE visit.
- i: Electrocardiograms will be performed at Screening (if applicable), Day -1 check-in, predose (within 60 min before the dose) and 2 hours (± 10 minutes) after the dose on Days 1, 30, 60, and 90, and at the EOE visit.

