Within each cohort of up to 16 subjects, subjects will be randomly assigned in a 3:1 to AT-007 and placebo. Subjects will receive study drug (AT-007 or placebo) on Day 1 and remain at the CRU for at least 24 hours after the first dose. Subjects will receive 1 daily dose of the same study drug (AT-007 or placebo) for a total of 90 consecutive days. In the extension, subjects will take most of their doses at home. Subjects will have 1 in-clinic stay associated with the first dose, a second in-clinic stay with the last dose, and out-patient visits at Months 1 and 2. Subjects will return for the EOE Visit at 28 days after the last dose.

Maximum duration of study participation (Screening through EOE Visit) for an individual subject will be approximately 158 days for a de novo subject and approximately 218 days for a subject who was screened for Part D, completed Part D, and completed Part D Extension without requiring a screening visit for the Part D Extension and without counting any washout period between Part D and Part D Extension.

Table 3-7: 90-Day Dose Cohort in Subjects with Classic Galactosemia (Part D Extension)

| Cohort | Dose | |
|--------|---|-------------|
| DE1 | AT-007 oral capsule on Day 1, dose 20 mg/kg (SAD portion), followed by AT-007 | placebo |
| | oral capsule QD for a total of 90 days, dose 20 mg/kg (n=up to 12) | (n=up to 4) |

n = number of subjects; MAD = multiple ascending dose; QD = once daily; SAD = single ascending dose. Note: There may be up to 1 additional cohort if the decision is made to test more than 1 dose level. Regardless of whether there is 1 or 2 cohorts, the maximum number of subjects is 16. However, the number of cohorts and total number of subjects may increase if doses above 40 mg/kg are tested in additional cohorts. The overall number of subjects per cohort may be increased to address any potential lost-to-follow-up among subjects treated with either placebo or AT-007.

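### Part D Extension completers are followed for adverse events to Day 91 or to about Day 118 depending on whether they enter the open-label study, so the crude TEAE rate depends on the share who switch

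*Protocol*

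**What the plan says.** Protocol Sections 7.1.1 and 8, and SAP 3.2.1, collect adverse events from consent through the EOS or EOE visit. In the Part D Extension the last dose is on Day 90 and the EOE visit falls 28 days later, on Day 118 ± 2.

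Subjects who move to the open-label study are exempt. Protocol Section 6.9 says "The EOE Visit will not be performed if subjects transition to the separate" open-label study, and adds "The study completion for these subjects will be the completion of the Treatment Period at Day 91". At the Day 91 discharge (Section 6.8.5) the EOE visit is scheduled "Only if subject is not directly entering the separate Open-Label Extension study". Sections 3.1, 3.3.6 and 4.5 and Appendix F footnote e agree.

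On analysis, Protocol Section 9.2.7 states: "TEAEs are defined as AEs with onset on or after the date/time of the first dose of study drug". The programming rule in SAP 7.12.2 likewise has a start and no stop. The SAP summarises TEAEs as numbers and percentages of subjects and as event counts. It has no common cut-off, no split between treatment and follow-up, and no exposure adjustment.

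The SAP does not mention the open-label study. In its Part D Extension text (3.1.4.6), subjects "return for the EOE Visit at 28 days after the last dose" without exception. The SAP says that it follows protocol version 6.0 and still gives 16 as the Extension maximum where the protocol has 28, so it may simply not have been updated.

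**The concern.** Because neither TEAE rule has an end, the end of data collection sets each subject's window, and that end depends on a decision taken around Day 90. Two completers with the same event process can have different chances of being counted, and the crude percentage shifts with the proportion who switch.

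Protocol Section 3.2 says that the visit 28 days after the last dose is there to capture the outcome of adverse events and those that start after treatment. For switchers nothing is scheduled in this study after Day 91. The EOE rows for laboratory tests, ECG and vital signs will therefore describe a subset, under a SAP that expects everyone to be in it.

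Safety is the primary endpoint. The Extension is the only placebo-controlled part with 90 days of dosing, and has at most 21 active and 7 placebo subjects.

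**Working it through.** **The plan's own durations.** The last dose is on Day 90, and 90 + 28 = Day 118, as stated. With 60 days of screening, 60 + 118 = 178 days for a de novo subject. With Part D first (40 days of screening and 60 study days), 40 + 60 + 118 = 218. Both match Protocol Section 3.3.6. For a switcher the same sums end at Day 91: 60 + 91 = 151, and 40 + 60 + 91 = 191.

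**Window length for completers.** 118 − 91 = 27 days; 27/118 = 22.9%; 118/91 = 1.30.

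**Effect on the chance of at least one TEAE.** The documents give no event rate. Assume a constant hazard *h* per day, the same on and off drug, so risk = 1 − exp(−*h* × days). The last column multiplies the gap by an assumed roll-over difference of 0.90 − 0.50 = 0.40, with no drug effect.

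| *h* per day | Risk by Day 91 | Risk by Day 118 | Gap (points) | Gap × 0.40 |
|---|---|---|---|---|
| 0.005 | 36.6% | 44.6% | 8.0 | 3.2 |
| 0.01 | 59.7% | 69.3% | 9.5 | 3.8 |
| 0.02 | 83.8% | 90.6% | 6.8 | 2.7 |

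**The same model over a wider range.** Start from an assumed 118-day risk *p*; the 91-day risk is then 1 − (1 − *p*)^(91/118).

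| *p* by Day 118 | Risk by Day 91 | Gap (points) | 90% vs 50% switching |
|---|---|---|---|
| 20% | 15.8% | 4.2 | 1.7 |
| 40% | 32.6% | 7.4 | 3.0 |
| 60% | 50.7% | 9.3 | 3.7 |
| 80% | 71.1% | 8.9 | 3.6 |

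**Dependence on the switch share.** The crude rate at switch share *s* is *s* × (91-day risk) + (1 − *s*) × (118-day risk). At *p* = 40% it is 40.0%, 38.1%, 36.3%, 34.4% and 32.6% for *s* = 0, 25, 50, 75 and 100%.

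**Post-treatment follow-up.** With 28 subjects and no dropout, 28 × (1 − *s*) have an EOE visit: 21, 14, 7 and 0 at *s* = 25, 50, 75 and 100%. At 75% that is about 5 active and 2 placebo. For an event with an assumed 10% post-treatment risk, the chance of seeing at least one case on active drug is 1 − 0.9^21 = 89% with 21 followed and 1 − 0.9^5 = 41% with 5.

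**After a common cut-off.** If onset is counted through last dose plus one day, every completer has 91 days and *s* drops out. The expected rates are then the 91-day column of the second table.

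**The case against.** Several points against this are fair.

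- *Size.* The 7 to 10 points compare a switcher with a non-switcher. A reader might take them as bias between arms, but that would need one arm to switch completely and the other not at all. At 90% versus 50% the difference is about 2 to 4 points. One of 7 placebo subjects is 14.3 points, so this is roughly a quarter of one subject. No inference on safety is planned.
- *Selection.* It is tempting to say that subjects with events will be the ones who do not roll over. The documents do not say who may or will enter the open-label study, or how that study collects adverse events.
- *Scope of the ratio.* The 1.30 applies to completers. Early discontinuers undergo the EOE procedures when they stop (Section 4.5), so some non-switchers may have shorter windows than switchers.
- *A contradiction between Sections 3.3.6 and 6.9.* Read alone, "For these subjects the EOE will be Day 91" might suggest that the EOE procedures are due on Day 91. The sentence just before it says that the visit is not required, so Day 91 is an end date and the two sections agree.
- *Missing assessments.* Section 6.8.4 already requires the physical examination, laboratory tests, UACR and UPCR, ECG and vital signs on Day 90. Repeating the full Section 6.9 set a day later would not change the 91 versus 118 day windows.
- *Parts D and E.* They have no such waiver, so the point does not extend to them.
- *Listings.* By-subject dosing and adverse event listings would let a reader pick out late-onset events by hand.

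What remains is that the planned summary tables mix two windows, and the SAP has no rule for them. Listings do not repair a table whose denominator is unsuited to part of its window.

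**Conclusion.** The point holds for the Part D Extension. As written, the crude TEAE percentage depends on the share of completers who switch, and scheduled safety data from Day 92 on come only from non-switchers, including some early discontinuers. Switchers do contribute adverse events, PK and biomarkers on Day 91 itself.

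The 27-day difference is firm for completers, within the ± 2 day visit window. The percentage-point figures rest on an assumed constant hazard and assumed roll-over shares, and would change if the event rate falls after dosing stops. If roll-over is equal in the two arms, both rates fall and the contrast changes little.

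No error rate or power is affected, because safety is descriptive. It is still the primary endpoint, and the remedy is cheap enough that the change should be made.

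**What to change.** In the SAP:

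1. Make the main Part D Extension TEAE, SAE and relatedness tables count onset from first dose through last dose plus one day, for every subject. Early discontinuers will still have shorter windows, but by the same rule.
2. Report later onset, including SAEs, in a separate post-treatment table whose denominator is the number actually followed beyond that point.
3. Tabulate roll-over to the open-label study by arm.
4. Correct SAP 3.1.4.6 to state that subjects entering the open-label study finish at Day 91 without an EOE visit.

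The data are already collected: onset date and time (Protocol Section 8, SAP 3.2.1) and the dosing record (Listing 16.2.5.1de). The cost is SAP wording, a roll-over tabulation and one extra adverse event table. The drawback is that delayed-onset events, which the EOE visit is meant to capture, move from the main table to the second, so the two should be presented together.

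Separately, the protocol should reconcile Day 91 vital signs. Appendix F footnote h says "Vital signs will be measured at Screening (if applicable), every check-in, every check-out", and Day 91 is a discharge day, but neither the Appendix F grid nor Section 6.8.5 lists them.

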6.10. Unscheduled Visit

An unscheduled visit may be performed at any time during the study at the subject's request or as deemed necessary by the Investigator/designee. At a minimum, concomitant medication data, AEs, and the date and reason for the unscheduled visit will be recorded. Other tests may be performed per Investigator/designee judgement.

7. STUDY ASSESSMENTS

Schedules of Assessments for Parts A, B, C, D, E, and D Extension are presented in [Appendix A](#), [Appendix B](#), [Appendix C](#), [Appendix D](#), [Appendix E](#), and [Appendix F](#), respectively. Procedures will be completed as specified in this protocol unless contraindicated due to a reported AE.

Assessments will be conducted within the time frames specified in the footnotes in the Schedules of Assessments.

7.1. Safety Assessments

7.1.1. Adverse Events

AEs will be monitored throughout the study. AEs will be collected for each subject from the time of informed consent through the EOS (or EOE) Visit. Subjects will be queried in a nonleading manner, without specific prompting (e.g., “Has there been any change in your health status since your last visit?”).

Safety reporting requirements are provided in [Section 8](#).

7.1.2. Clinical Laboratory Tests

Blood and urine samples for routine clinical laboratory tests will be collected at the visits as indicated in the Schedules of Assessments for Parts A, B, C, D, E, and D Extension ([Appendix A](#), [Appendix B](#), [Appendix C](#), [Appendix D](#), [Appendix E](#), and [Appendix F](#), respectively).

A Clinical Laboratory Improvement Amendments (CLIA) certified laboratory will perform the following clinical laboratory tests:

- Hematology: hemoglobin, hematocrit, total and differential leukocyte count, RBC, and platelet count
- Serum Chemistry: albumin, blood urea nitrogen (BUN), creatinine, total bilirubin, alkaline phosphatase (ALP), aspartate transaminase (AST), alanine transaminase (ALT), sodium (Na⁺), potassium (K⁺), chloride (Cl⁻), lactate dehydrogenase (LDH), calcium (Ca), uric acid, glucose, direct bilirubin (DB), and gamma-glutamyl transferase (GGT)
- Coagulation: prothrombin time (PT) and international normalized ratio (INR)
- Serology: blood tests for hepatitis B surface antigen, hepatitis C antibody, and HIV
- Urinalysis by an automated or manual urine “dipstick” method: pH, specific gravity, protein, glucose, ketones, bilirubin, blood, nitrite, leukocyte esterase, and urobilinogen. If protein, occult blood, nitrite, or leukocyte esterase values are out of range, a microscopic examination will be performed.
- Urine Drug Screen: drugs of abuse (amphetamines, benzodiazepines, barbiturates, cannabinoids, cocaine, opiates)
- Urinary markers of renal function: UACR and UPCR
- Urine cotinine screen (subjects in Parts A, B, and C only)

- Pregnancy test (all female subjects of childbearing potential)
- FSH (for female subjects claiming postmenopausal status)

For Parts D, E, and D Extension only, the following tests will be done in addition to the ones listed above:

- GALT (Part D and Part D Extension but only done once for subjects participating in both Parts) or GALK (Part E) activity in red blood cells
- GALT (Part D and Part D Extension but only done once for subjects participating in both Parts) or GALK (Part E) gene analysis
- Aldose Reductase activity (only done once for subjects participating in both Parts D and D Extension)

7.1.3. Physical Examinations

Physical examinations will be performed at the visits as indicated in the Schedules of Assessments for Parts A, B, C, D, E, and D Extension ([Appendix A](#), [Appendix B](#), [Appendix C](#), [Appendix D](#), [Appendix E](#), and [Appendix F](#), respectively). Height will be measured at the Screening Visit only. Weight will be measured as part of all physical examinations. Any time during the study after the first dose of study drug, abnormal findings considered to be clinically significant by the Investigator/designee will be reported as AEs.

7.1.4. Vital Signs

Vital signs (blood pressure, pulse rate, respiration rate, and temperature) will be measured at the visits as indicated in the Schedules of Assessments for Parts A, B, C, D, E, and D Extension ([Appendix A](#), [Appendix B](#), [Appendix C](#), [Appendix D](#), [Appendix E](#), and [Appendix F](#), respectively). Additional vital signs measurements may be taken as deemed medically necessary by the Investigator/designee. For purposes of qualifying any given subject for study participation, out of range vital signs may be repeated once.

All vital signs measurements will be taken with the subject in a seated position and after the subject has been resting in that seated position for at least 5 minutes. Any time during the study after the first dose of study drug, abnormal vital sign measurements considered to be clinically significant by the Investigator/designee will be reported as AEs.

7.1.5. Electrocardiograms (ECGs)

ECGs will be performed at the visits as indicated in the Schedules of Assessments for Parts A, B, C, D, E, and D Extension ([Appendix A](#), [Appendix B](#), [Appendix C](#), [Appendix D](#), [Appendix E](#), and [Appendix F](#), respectively). All ECGs will be done with the subject in a supine position and after the subject has been resting in that supine position for at least 5 minutes.

7.1.6. Prior and Concomitant Medications

Prior medications and concomitant medications will be collected throughout the study from the signing of informed consent through the EOS (or EOE) Visit. For each medication (prescription and OTC medication [including nutritional or dietary supplements, herbal preparations, or

vitamins]), start and stop dates, dosage regimen (dose plus route and frequency of administration), and indication will be recorded.

7.1.7. Pregnancy

Pregnancies will not be documented or reported as AEs. However, if at any time the pregnancy falls under the scope and definition of a SAE ([Section 8.1.2](#)), it will then be reported as such.

7.1.8. Other Safety Measures

Medical emergency personnel trained in advanced cardiac life support will be on site to monitor subjects during the confinement period in the CRU. Emergency medical equipment including, but not limited to, intubation equipment and pulse oximetry shall be maintained on site to administer appropriate medical care should it be required.

Appropriate drugs and medical equipment to treat acute [hypotensive, bronchoconstrictive, or anaphylactic] reactions must be immediately available at study centers. Study personnel must be trained to recognize and treat these reactions.

The reason for any use of these emergency personnel/equipment or measures to treat acute reactions must be reported as an AE (or SAE, if appropriate).

7.2. Pharmacokinetic (PK) Assessments

Blood and/or urine samples for PK assessments will be collected at the visits as indicated in the Schedules of Assessments for Parts A, B, C, D, E, and D Extension ([Appendix A](#), [Appendix B](#), [Appendix C](#), [Appendix D](#), [Appendix E](#), and [Appendix F](#), respectively). Instructions for collecting and processing blood and urine samples for AT-007 and possible AT-007 metabolite analysis will be provided in a separate laboratory manual. Plasma samples will be analyzed for AT-007 using a validated method. PK samples will be stored for possible future analysis of AT-007 metabolites.

Also, for subjects in Part C, a Day 7 lumbar puncture will be done to collect CSF for AT-007 measurement ([Appendix C](#)) using a qualified assay.

The PK parameters in [Table 8](#) will be determined for the SAD parts of the study (i.e., Part A, the single dose period of Parts D and E).

Table 8: PK Parameters of AT-007 After a Single Dose in Healthy Subjects (Part A) and Subjects with Classic Galactosemia (SAD Period of Parts D and E)

PK Parameter	Definition
C_{max}	Maximum concentration, determined directly from individual concentration time data
T_{max}	Time of the maximum concentration
λ_z	The observed terminal rate constant; estimated by linear regression through at least 3 data points in the terminal phase of the log concentration-time profile
$T_{1/2}$	The observed terminal half-life, calculated as: $T_{1/2} = \frac{\ln(2)}{\lambda_z}$
AUC_{last}	Area under the concentration-time curve from time-zero to the time of the last quantifiable concentration; calculated using the linear trapezoidal rule
AUC_{inf}	Area under the concentration-time curve from time-zero extrapolated to infinity; calculated as: $AUC_{inf} = AUC_{last} + \frac{C_{last}}{\lambda_z}$
$AUC_{Extrap} (\%)$	The percentage of AUC_{inf} based on extrapolation
C_{last}	The last quantifiable concentration determined directly from individual concentration-time data
T_{last}	Time of the last quantifiable concentration
CL/F	Clearance after extravascular administration, calculated as: $CL/F = \text{Dose}/AUC_{inf}$
Vz/F	Volume of distribution in the terminal phase, calculated as: $Vz/F = (CL/F)/\lambda_z$

The PK parameters in [Table 9](#) will be determined for the multiple dosing parts of the study (i.e., Part B, Part C, MAD period in Parts D and E, and Part D Extension).

Table 9: PK Parameters of AT-007 During Multiple Dosing in Healthy Subjects (Parts B and C) and Subjects with Galactosemia (MAD Period of Parts D and E and Part D Extension)

PK Parameter	Definition
C_{max}	Maximum concentration, determined directly from individual concentration time data (Day 1 and Day of Last Dose)
T_{max}	Time of the maximum concentration (Day 1 and Day of Last Dose)
λ_z	The observed terminal rate constant; estimated by linear regression through at least 3 data points in the terminal phase of the log concentration-time profile (Day of Last Dose only)
$T_{1/2}$	The observed terminal half-life, calculated as: $T_{1/2} = \frac{\ln(2)}{\lambda_z}$ (Day of Last Dose only)
AUC_{tau}	Area under the concentration-time curve during the 24-hour dosing interval; calculated using the linear trapezoidal rule (Day 1 and Day of Last Dose) Note: If quantifiable data are not observed through 24 h postdose, AUC_{tau} will be estimated using extrapolation (from the time of the last reported concentration to 24 h) and AUC_{last} will also be reported.
AUC_{last}	Area under the concentration-time curve from time-zero to the time of the last quantifiable concentration; calculated using the linear trapezoidal rule (Day of Last Dose; Day 1 if quantifiable data are not observed through 24 h postdose)
AUC_{inf}	Area under the concentration-time curve from time-zero extrapolated to infinity; calculated as: $AUC_{inf} = AUC_{last} + \frac{C_{last}}{\lambda_z}$ (Day of Last Dose only)
$AUC_{Extrap} (\%)$	The percentage of AUC_{inf} based on extrapolation (Day of Last Dose only)
C_{last}	The last quantifiable concentration determined directly from individual concentration-time data (Day 1 and Day of Last Dose)
T_{last}	Time of the last quantifiable concentration (Day 1 and Day of Last Dose)
CL/F	Clearance after extravascular administration, calculated as: CL/F = Dose/ AUC_{tau} (Day X), where Day X = Day of Last Dose and Dose is the actual dose administered (mg/kg x kg). (Day of Last Dose only) Note: CL/F/kg may also be reported
Vz/F	Volume of distribution in the terminal phase, calculated as: Vz/F = (CL/F)/ λ_z (Day of Last Dose only) Note: Vz/F/kg may also be reported
Rac	The accumulation ratio during multiple dose administration, based on C_{max} and AUC_{tau} ; calculated as: Rac (AUC_{tau}) = AUC_{tau} (Day X) / AUC_{tau} (Day 1) Rac (C_{max}) = C_{max} (Day X) / AUC_{tau} (Day 1) Note: Rac will be tabulated with the pharmacokinetic parameters on Day X. Note: Day X = Day of Last Dose

Note: Day of Last Dose is Day 7 in Parts B and C, Day 32 in the MAD portion of Parts D and E, and Day 90 in Part D Extension.

